**5.0 Grouping Factor: None****6.0 Registration Procedures****6.1 Registration Procedures**

6.11 To register a patient, access the Mayo Clinic Cancer Center (MCCC) web page and enter the remote registration/randomization application. The registration/randomization application is available 24 hours a day, 7 days a week. Back up and/or system support contact information is available on the Web site. If unable to access the Web site, call the MCCC Registration Office at [REDACTED] between the hours of 8 a.m. and 5:00 p.m. Central Time (Monday through Friday).

The instructions for the registration/randomization application are available on the MCCC web page [REDACTED] and detail the process for completing and confirming patient registration. Prior to initiation of protocol treatment, this process must be completed in its entirety and a MCCC subject ID number must be available as noted in the instructions. It is the responsibility of the individual and institution registering the patient to confirm the process has been successfully completed prior to release of the study agent. Patient registration via the registration/randomization application can be confirmed in any of the following ways:

- Contact the MCCC Registration Office [REDACTED] If the patient was fully registered, the MCCC Registration Office staff can access the information from the centralized database and confirm the registration.
- Refer to "Instructions for Remote Registration" in section "Finding/Displaying Information about A Registered Subject."

**6.12 Correlative Research: (See Section 14.)**

A mandatory correlative research component is part of this study, the patient will be automatically registered onto this component (see Sections 3.19c and 14.1).

**6.13 Prior to accepting the registration, registration/randomization application will verify the following:**

- IRB approval at the registering institution
- Patient eligibility
- Existence of a signed consent form
- Existence of a signed authorization for use and disclosure of protected health information

**6.14 Documentation of IRB approval must be on file in the Registration Office before an investigator may register any patients.**

In addition to submitting initial IRB approval documents, ongoing IRB approval documentation must be on file (no less than annually) at the Registration Office [REDACTED] If the necessary documentation is not submitted in advance

of attempting patient registration, the registration will not be accepted and the patient may not be enrolled in the protocol until the situation is resolved.

When the study has been permanently closed to patient enrollment, submission of annual IRB approvals to the Registration Office is no longer necessary.

- 6.15 At the time of registration, the following will be recorded:
  - Patient has/not given permission to store and use his/her sample(s) for future research of Multiple Myeloma at Mayo.
  - Patient has/not given permission to store and use his/her sample(s) for future research to learn, prevent, or treat other health problems.
  - Patient has/not given permission for MCCC to give his/her sample(s) to researchers at other institutions.
- 6.16 Treatment on this protocol must commence at a Mayo Clinic Institution, under the supervision of a hematologist.
- 6.17 Treatment cannot begin prior to registration and must begin ≤ 14 days after registration.
- 6.18 Pretreatment tests/procedures (see Section 4.0) must be completed within the guidelines specified on the test schedule.
- 6.19 All required baseline symptoms (see Section 10.61) must be documented and graded.
- 6.19a Blood draw kit is available on site, if applicable (see Section 14).

## 6.2 Study Conduct

The clinical trial will be conducted in compliance with regulations (21 CFR 312, 50, and 56), guidelines for Good Clinical Practice (ICH Guidance E6), and in accordance with general ethical principles outlined in the Declaration of Helsinki; informed consent will be obtained from all participating patients; the protocol and any amendments will be subject to approval by the designated IRB prior to implementation, in accordance with 21 CFR 56.103(a); and subject records will be stored in a secure location and subject confidentiality will be maintained. The investigator will be thoroughly familiar with the appropriate use of the study drug as described in the protocol and Investigator's Brochure. Essential clinical documents will be maintained to demonstrate the validity of the study and the integrity of the data collected. Master files should be established at the beginning of the study, maintained for the duration of the study and retained according to the appropriate regulations.

## 7.0 Protocol Treatment

### 7.1 Treatment Schedule

Cycle length: 84 days.

Agent	Route	Dose	Day	Retreatment
Ixazomib	PO	4 mg	1, 8, 15, 29, 36, 43, 57, 64, 71	Every 84 days
Pembrolizumab	IV	200mg	Day 1, 22, 43, 64	Every 84 days
Dexamethasone	PO	40 mg	1, 8, 15, 29, 36, 43 57, 64, 71	Every 84 days

7.2 For this protocol, the patient must return to the consenting institution (Mayo Clinic) for evaluation at least every 21 days ( $\pm$  1 day). Treatment by a local medical doctor (LMD) is not allowed. Note: If patient is stable after 2 cycles, physical exam can be reduced to Weeks 1 and 7 of each cycle.

7.3 Patients are allowed to collect stem cells after 1 cycle of initial therapy. Stem cells can be collected using standard institutional protocols. Any delay beyond 4 weeks should be discussed with the study PI prior to reinitiating protocol therapy.

7.4 Patients should be instructed to swallow ixazomib capsules whole, with water, and not to break, chew, or open the capsules. The ixazomib should be taken on an empty stomach (no food or drink apart from 240 mL of water), at least 1 hour before or no sooner than 2 hours after food. Each capsule should be swallowed separately with a sip of water. A total of approximately 240 mL (about 1 cup/8 oz) of water should be taken with the capsules.

Missed doses can be taken as soon as the patient remembers as long as the next scheduled dose is 72 hours or more away. Patients who vomit a dose after ingestion will not receive an additional dose, but should resume dosing at the time of the next scheduled dose.

Drug will be administered only to eligible patients under the supervision of the investigator or identified sub-investigator(s). The drug will be prepared under the supervision of a pharmacist, or appropriately qualified and trained personnel.

7.5 Dexamethasone (Cycles 1-4, maximum of 1 year)

- Dexamethasone may be self-administered by the subject on an outpatient basis.
- Missed doses of dexamethasone will not be made up. Procedures for dose reductions and delays are summarized in Section 8.0.
- Dexamethasone is commercially available. Accurate records will be kept in the source documents of all drug administration (including dispensing and dosing).

## 8.0 Dosage Modification Based on Adverse Events

Individual drugs can be dose reduced as per the table below depending on the adverse event attribution of possible, probable, or definite. If multiple adverse events are seen, administer dose based on greatest reduction required for any single adverse event observed. Reductions apply to treatment given in the preceding cycle and are based on adverse events observed since the prior dose.

**ALERT:** *ADR reporting may be required for some adverse events (See Section 10)*

### 8.1 Dose Levels for each drug in the combination.

	Ixazomib (Days 1, 8, 15, , 29, 36, 43, 57, 64, 71)	Pembrolizumab (200 mg/dose)	Dexamethasone (Days 1, 8, 15, 29, 36, 43, 57, 64, 71)
Starting dose	4 mg	Day 1, 22, 43, 64	40 mg
-1	3 mg	Day 1 and 43	20 mg
-2	2.3 mg	Discontinue	12 mg

\*See Table 8.2 below

**Note: If ixazomib is discontinued, the patient will discontinue pembrolizumab and dexamethasone and go to event monitoring.**

### 8.11 Instruction for initiation of a new cycle of therapy

A new cycle of treatment may begin on the scheduled Day 1 of a new cycle if:

- The ANC is  $\geq 1000/\mu\text{L}$
- The platelet count is  $\geq 75,000/\mu\text{L}$
- Any other non-hematologic drug-related (possible, probable, or definite) adverse event that may have occurred has resolved to  $\leq$ Grade 1 or baseline severity.

If these conditions are not met on Day 1 of a new cycle, dosing should be delayed for 1 week. At the end of that time, the patient should be re-evaluated to determine whether the criteria have been met. If the patient continues to fail to meet the above-cited criteria, delay therapy and continue to re-evaluate.

If any drug dosing was halted during the previous cycle and was restarted with a one-level dose reduction without requiring an interruption for the remainder of the cycle, then that reduced dose level will be initiated on Day 1 of the new cycle.

If any drug dosing was omitted for the remainder of the previous cycle or if the new cycle is held due to known hematologic toxicity newly encountered on the scheduled Day 1, then the new cycle will be started with a one-level dose reduction. If a new cycle of therapy cannot be restarted within 4 weeks of the scheduled Day 1 due to non-resolution of drug related toxicities, the patient will be removed from protocol therapy and will go to event monitoring.

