### 8.2 Dose modifications for pembrolizumab based on adverse events during a cycle

CTCAE System/Organ/Class (SOC)	Adverse Event	Omit Treatment for Grade	Timing for Restarting Treatment	Treatment Discontinuation
Endocrine disorders	Endocrine disorders – Other, specify: Hypophysitis	2-4	AE resolves to Grade 0-1. Therapy with pembrolizumab can be continued while endocrine replacement therapy is instituted	AE does not resolve within 12 weeks of last dose or inability to reduce corticosteroid to 10 mg or less of prednisone or equivalent per day within 12 weeks
Endocrine disorders	Hyperthyroidism	3	AE resolves to Grade 0-1	AE does not resolve within 12 weeks of last dose or inability to reduce corticosteroid to 10 mg or less of prednisone or equivalent per day within 12 weeks
		4	Permanently discontinue	Permanently discontinue
Endocrine disorders	Hypothyroidism	2	Therapy with pembrolizumab can be continued while thyroid replacement therapy is instituted	Therapy with pembrolizumab can be continued while thyroid replacement therapy is instituted
Gastrointestinal disorders	Diarrhea or Colitis	2-3	AE resolves to Grade 0-1	AE does not resolve within 12 weeks of last dose or inability to reduce corticosteroid to 10 mg or less of prednisone or equivalent per day within 12 weeks
		4	Permanently discontinue	Permanently discontinue
General disorders and administration site conditions	Infusion related reaction	2 b	AE resolves to Grade 0-1	Permanently discontinue if AE develops despite adequate premedication
		3-4	Permanently discontinue	Permanently discontinue
Investigations	Aspartate aminotransferase (AST) increased or Alanine aminotransferase (ALT) increased or Blood bilirubin increased	2	AE resolves to Grade 0-1	AE does not resolve within 12 weeks of last dose
		3-4	Permanently discontinue (see exception below) a	Permanently discontinue
Metabolism and nutrition disorders	Glucose intolerance (Type 1 diabetes mellitus [if new onset]) or Hyperglycemia	3-4	Omit pembrolizumab for new onset Type 1 diabetes mellitus or Grade 3-4 hyperglycemia associated with evidence of beta cell failure	Resume pembrolizumab when patients are clinically and metabolically stable

CTCAE System/Organ/Class (SOC)	Adverse Event	Omit Treatment for Grade	Timing for Restarting Treatment	Treatment Discontinuation

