### 8.3 Dose modifications for Ixazomib based on adverse events during a cycle

CTCAE System/Organ/Class (SOC)*	ADVERSE EVENT	ACTION**
Investigations	Neutrophil count decreased $<1.0 \times 10^9/L$ or Neutrophil count decreased $>1.0 \times 10^9/L$ (up to LLN) and Fever (temperature $>38.5^{\circ}C$ ) or Platelet count decreased $<30 \times 10^9/L$	Days 2-84: Ixazomib dose should be omitted on Days 1, 8, 15, 29, 36, 43, 57, 64, 71 as applicable Complete blood count (CBC) with differential should be followed weekly If ANC is $\geq 1.0 \times 10^9/L$ and/or platelet counts $\geq 30 \times 10^9/L$ , ixazomib may be reinitiated with 1 dose level reduction. The subsequent cycle will use the reduced dose.
Nervous System Disorders	Newly developed peripheral sensory neuropathy Grade 1 with pain or Peripheral sensory neuropathy Grade 2	Omit until resolution to Grade $<1$ or baseline No dose reduction necessary for this grade
	Peripheral sensory neuropathy with pain Grade 2 or Peripheral sensory neuropathy Grade 3	Omit ixazomib until toxicity resolves or returns to baseline. When toxicity resolves, re-initiate ixazomib at the next lower dose level.
	Peripheral sensory neuropathy Grade 4	Discontinue ixazomib. Peripheral neuropathy should be monitored until toxicity resolves or returns to baseline.
Skin and subcutaneous tissue disorders	Rash, maculo-papular, $\geq$ Grade 2	Omit ixazomib until rash resolves to $\leq$ Grade 1 (See Section 9.9a ). Restart at same dose. If the rash recurs, reduce dose by one dose level.
	Any other skin AE, Grade 4	Discontinue ixazomib and remove patient from all study treatment
	Any other Grade 3 attributable adverse event except: 
 
• Nausea and/or Vomiting Grade 3 in the absence of optimal anti-emetic prophylaxis
 
• Diarrhea Grade 3 that occurs in the absence of optimal supportive therapy
 
• Fatigue Grade 3
 
• Anemia
 
• White blood cell decreased
 
• Lymphocyte count decreased
 
	Omit ixazomib depending on the attribution, until resolution to Grade $\leq 1$ or baseline Restart at next lower dose. If a patient is already at the lowest drug level, go to event monitoring
	Any other Adverse Events Grade 4	Consider permanently discontinuing ixazomib – Exception if the investigator determines the patient is obtaining a clinical benefit

\* Located at [REDACTED]

\*\* Use the following to describe actions in the Action column:

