Subjects should receive appropriate supportive care measures as deemed necessary by the treating investigator. Suggested supportive care measures for the management of adverse events with potential immunologic etiology are outlined below. Where appropriate, these guidelines include the use of oral or intravenous treatment with corticosteroids as well as additional anti-inflammatory agents if symptoms do not improve with administration of corticosteroids. Note that several courses of steroid tapering may be necessary as symptoms may worsen when the steroid dose is decreased. For each disorder, attempts should be made to rule out other causes such as metastatic disease or bacterial or viral infection, which might require additional supportive care. The treatment guidelines are intended to be applied when the investigator determines the events to be related to pembrolizumab.

Note: if after the evaluation the event is determined not to be related, the investigator does not need to follow the treatment guidance (as outlined below). Refer to Table 8.2 for dose modification.

It may be necessary to perform conditional procedures such as bronchoscopy, endoscopy, or skin photography as part of evaluation of the event.

- **Pneumonitis:**

- For **Grade 2 events**, treat with systemic corticosteroids. When symptoms improve to Grade 1 or less, steroid taper should be started and continued over no less than 4 weeks.
- For **Grade 3-4 events**, immediately treat with intravenous steroids. Administer additional anti-inflammatory measures, as needed.

- Add prophylactic antibiotics for opportunistic infections in the case of prolonged steroid administration.
- **Diarrhea/Colitis:**

Subjects should be carefully monitored for signs and symptoms of enterocolitis (such as diarrhea, abdominal pain, blood or mucus in stool, with or without fever) and of bowel perforation (such as peritoneal signs and ileus).

  - All subjects who experience diarrhea/colitis should be advised to drink liberal quantities of clear fluids. If sufficient oral fluid intake is not feasible, fluid and electrolytes should be substituted via IV infusion. For Grade 2 or higher diarrhea, consider GI consultation and endoscopy to confirm or rule out colitis.
  - For **Grade 2 diarrhea/colitis**, administer oral corticosteroids.
  - For **Grade 3 or 4 diarrhea/colitis**, treat with intravenous steroids followed by high dose oral steroids.

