  - When symptoms improve to Grade 1 or less, steroid taper should be started and continued over no less than 4 weeks.
- **Type 1 diabetes mellitus (if new onset, including diabetic ketoacidosis [DKA]) or ≥ Grade 3 Hyperglycemia, if associated with ketosis (ketonuria) or metabolic acidosis (DKA)**
  - For **T1DM** or **Grade 3-4 Hyperglycemia**
    - Insulin replacement therapy is recommended for Type I diabetes mellitus and for Grade 3-4 hyperglycemia associated with metabolic acidosis or ketonuria.
    - Evaluate patients with serum glucose and a metabolic panel, urine ketones, glycosylated hemoglobin, and C-peptide.
- **Hypophysitis:**
  - For **Grade 2** events, treat with corticosteroids. When symptoms improve to Grade 1 or less, steroid taper should be started and continued over no less than 4 weeks. Replacement of appropriate hormones may be required as the steroid dose is tapered.
  - For **Grade 3-4** events, treat with an initial dose of IV corticosteroids followed by oral corticosteroids. When symptoms improve to Grade 1 or less, steroid taper should be started and continued over no less than 4 weeks. Replacement of appropriate hormones may be required as the steroid dose is tapered.
- **Hyperthyroidism or Hypothyroidism:**

Thyroid disorders can occur at any time during treatment. Monitor patients for changes in thyroid function (at the start of treatment, periodically during treatment, and as indicated based on clinical evaluation) and for clinical signs and symptoms of thyroid disorders.

  - **Grade 2** hyperthyroidism events (and **Grade 2-4** hypothyroidism):
    - In hyperthyroidism, non-selective beta-blockers (e.g. propranolol) are suggested as initial therapy.
    - In hypothyroidism, thyroid hormone replacement therapy, with levothyroxine or liothyroinine, is indicated per standard of care.
  - **Grade 3-4** hyperthyroidism

- Treat with an initial dose of IV corticosteroid followed by oral corticosteroids. When symptoms improve to Grade 1 or less, steroid taper should be started and continued over no less than 4 weeks. Replacement of appropriate hormones may be required as the steroid dose is tapered.
- **Hepatic:**
  - For **Grade 2** events, monitor liver function tests more frequently until returned to baseline values (consider weekly).
    - Treat with IV or oral corticosteroids
  - For **Grade 3-4** events, treat with intravenous corticosteroids for 24 to 48 hours.

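### Section 8.11 has no exception for Grade 2 hypothyroidism on thyroid replacement, so it can delay, and after 4 weeks end, a regimen that Table 8.2 lets continue

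*Combined protocol and SAP*

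**What the plan says.** **Starting a cycle (section 8.11).** The third start condition is "Any other non-hematologic drug-related (possible, probable, or definite) adverse event that may have occurred has resolved to" Grade 1 or less, or to baseline severity. No event is exempted. Then: "If these conditions are not met on Day 1 of a new cycle, dosing should be delayed for 1 week", with further delay and re-evaluation while the condition still fails. The end point is also fixed: "If a new cycle of therapy cannot be restarted within 4 weeks of the scheduled Day 1 due to non-resolution of drug related toxicities", treatment under the protocol stops and event monitoring begins.

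**During a cycle (Table 8.2).** For Grade 2 hypothyroidism, the restart cell and the discontinuation cell carry the same sentence: "Therapy with pembrolizumab can be continued while thyroid replacement therapy is instituted". Neither asks for a return to Grade 0-1, and neither sets a time limit.

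**Supportive care (section 9.9h).** For pembrolizumab-related events the site is told "Refer to Table 8.2 for dose modification". For the event itself: "In hypothyroidism, thyroid hormone replacement therapy, with levothyroxine or liothyroinine, is indicated per standard of care". Nothing there stops a study drug.

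**The other two drugs.** For events it does not list by name, Table 8.3 acts on ixazomib only from Grade 3 ("Any other Grade 3 attributable adverse event except" a short list). Table 8.4 has no thyroid row for dexamethasone.

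**The concern.** During a cycle, the tables read together stop no drug for Grade 2 hypothyroidism on replacement. At the next cycle start, 8.11 applies a general resolution rule to the same event and holds the whole regimen. No text says which rule prevails.

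At stake is the treatment of an individual patient. Someone whom the event-specific rule means to keep on therapy could be delayed and, if the grade does not fall, lose all three drugs for an event already being managed with replacement. Two clinicians could also treat identical patients differently, depending on which section they follow.

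**Working it through.** The plan gives no figure to reproduce. The check sets the rules side by side and then works out dates, doses and an assumed frequency.

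**1. Same patient, same event: drug-related hypothyroidism, Grade 2, above baseline, on replacement**

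| Visit | Governing text | Result |
|---|---|---|
| Day 64 (pembrolizumab due) | Table 8.2, hypothyroidism row | Pembrolizumab may be given |
| Day 64 (ixazomib, dexamethasone due) | Tables 8.3 and 8.4 | No action triggered |
| Next cycle's Day 1 (all three due) | 8.11, third bullet | All three delayed |
| Four weeks after that Day 1, still Grade 2 | 8.11, last paragraph | Off protocol treatment |

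If the event is graded 1 or less, or is back at baseline severity, 8.11 passes and the conflict disappears.

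**2. Dates (section 7.1: 84-day cycle)**
- Next scheduled Day 1: 84 + 1 = Day 85.
- Four-week limit: 85 + 28 = Day 113, which is (113 - 1)/7 = 16 weeks after the first dose.
- Time since the Day 64 pembrolizumab dose, if given: 113 - 64 = 49 days, or 7 weeks.

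**3. Doses at issue**
- The definitions under Tables 8.2 to 8.4 say that delayed doses are made up. A cycle that starts one to three weeks late therefore costs time, not doses.
- On removal at Day 113, the cycle 2 doses due on Days 85 to 112 are not given:
  - ixazomib on cycle Days 1, 8, 15 = Days 85, 92, 99: 3 doses (the next, cycle Day 29, falls on Day 113);
  - dexamethasone on the same days: 3 doses;
  - pembrolizumab on cycle Days 1, 22 = Days 85, 106: 2 doses (the next, cycle Day 43, falls on Day 127).
- All later treatment is lost as well.

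**4. Response assessment**
- Section 4.1 schedules electrophoresis on Days 22, 43, 64 and 85 and at end of treatment: 4 + 1 = 5 post-baseline evaluations in the removal case.
- Footnote a of Table 11.5 accepts two consecutive assessments at any time before new therapy. A response first seen by Day 85 can still be confirmed at the end-of-treatment evaluation if no new therapy has begun.
- Section 16.311 keeps eligible, treated patients in the denominator unless they are major violations.

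**5. Frequency**
- Section 15.27 lists hypothyroidism for pembrolizumab at 1% to under 10%, with no grade stated and not for this combination.
- Assuming that the range covers all grades and carries over: 37 x 0.01 = 0.37, and 37 x 0.10 = 3.7. The expected number is from 0.37 to fewer than 3.7 of 37 patients.
- Cases still Grade 2 on a Day 1, and still so four weeks later, would be a subset. The documents give nothing from which to size it.

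**The case against.** **The rules have different scopes.** Table 8.2 is headed as covering events within a cycle, and 8.11 covers the start of one. A stricter Day 1 check is a pattern here: Table 8.3 lets ixazomib resume at platelets of 30 x 10^9/L, while a new cycle needs 75,000/µL; Grade 3 fatigue is excepted in Table 8.3 but not in 8.11. The pattern is real, but it does not reconcile these two texts. Pembrolizumab is due on Day 1 of every cycle, and the hypothyroidism permission has no end point.

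**Table 8.2 is itself unclear.** Grade 2 sits in the column of grades at which treatment is omitted, and the permission names pembrolizumab only. Both are fair observations. Still, neither action cell tells the site to omit a dose, and no table stops the other two drugs for this event.

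**The trigger is unproven.** This stands. The protocol grades by CTCAE v4.0 but does not reproduce the scale or say what grade a patient controlled on replacement carries. Removal needs an event that is drug-related, Grade 2, above baseline, present on Day 1 and unresolved four weeks later.

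**Stronger readings that the documents do not support.** A reader might infer that every delay costs doses; the hold/delay definition says otherwise. A reader might take 3.7 of 37 as a documented ceiling; it rests on two assumptions. A reader might think that 8.11 contradicts Table 8.2 for endocrine events in general. The hypophysitis row says "AE resolves to Grade 0-1. Therapy with pembrolizumab can be continued while endocrine replacement therapy is instituted", so it also asks for resolution. The diabetes and hyperglycemia row does allow pembrolizumab to resume on stability, without naming a grade, but only after omission for a Grade 3-4 event. Whether to relax the Day 1 check there is a separate clinical judgement.

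**Conclusion.** The conflict in the text is clear. For drug-related hypothyroidism still at Grade 2 and above baseline, 8.11 directs delay of all three drugs and then removal, while the event-specific row of Table 8.2 sets neither a resolution requirement nor a time limit.

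Confidence in the consequence is lower. It depends on how controlled disease is graded and on how often Grade 2 persists, and the documents give neither. Few patients are likely to be affected, on the stated assumption about the listed range.

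One might infer that the trial's conclusion is at risk. It is not: sample size, error rates and the decision rule are unaffected, and the effect on the response rate should be small. This is a cheap improvement that protects individual patients and makes handling consistent.

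**What to change.** Add to the end of the third bullet of section 8.11: *except Grade 2 hypothyroidism managed with thyroid replacement therapy, as allowed in Table 8.2*.

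Keep the exception that narrow, and do not extend it to hypophysitis or other endocrine events. The hypophysitis row covers Grades 2-4, so a wider exception could let all three drugs restart with unresolved Grade 3-4 disease. Grade 3-4 hypothyroidism stays under 8.11 as now.

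The cost is one line of amendment wording and a slightly looser Day 1 check for this one event. Visits, sample size and analysis do not change.

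### Section 8.11 and Table 8.3 give different ixazomib doses when certain events run to the end of a cycle, and the pembrolizumab consequence is left unsettled

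*Combined protocol and SAP*

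**What the plan says.** Section 8.11 governs the start of a new cycle and has two clauses on earlier interruptions.

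- A drug that was halted and "was restarted with a one-level dose reduction without requiring an interruption for the remainder of the cycle" keeps its reduced level on the next Day 1.
- "If any drug dosing was omitted for the remainder of the previous cycle", or if the new cycle is held for newly found hematologic toxicity, "then the new cycle will be started with a one-level dose reduction". The clause names no event, grade or drug.

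Table 8.3 sets ixazomib actions by event. For new Grade 1 sensory neuropathy with pain, or Grade 2, ixazomib is omitted and then "No dose reduction necessary for this grade". For maculo-papular rash of Grade 2 or more, it is omitted until improvement and then: "Restart at same dose. If the rash recurs, reduce dose by one dose level". Section 9.9a, to which that row refers, says that ixazomib is resumed below the level at which the rash appeared.

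Table 8.2 sets pembrolizumab actions. Its restart column is about timing, and the usual entry is "AE resolves to Grade 0-1". Table 8.1 defines a pembrolizumab level -1 (infusions on Days 1 and 43 only) and a level -2 (stop).

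Section 7.1 puts the last ixazomib dose of the 84-day cycle on Day 71 and the last pembrolizumab infusion on Day 64. The notes under the tables define an omitted dose as one that is skipped and not made up.

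**The concern.** A patient can meet the 8.11 condition and, for the same event, an event row that says the opposite. Both are express instructions. Staff who follow one section will give a different ixazomib dose from staff who follow the other, and neither would be deviating from the protocol.

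The primary goal (Section 2.1) concerns pembrolizumab with standard doses of ixazomib and dexamethasone. If delivered dose depends on which passage was read, safety management is inconsistent, and it is less clear what exposure lies behind the observed response rate.

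**Working it through.** No figure in Section 16 is at issue. As a context check, exact binomial calculation of the stated design (stop at 4 or fewer of 14; success at 15 or more of 37) gives 0.0954 at a true rate of 30% and 0.8526 at 50%. These match the stated .095 and 0.853.

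**1. Row by row.** Table 8.3 has five rows that allow restart with a dose instruction. Suppose in each case that ixazomib was omitted through Day 71.

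| Event row | Restart dose in Table 8.3 | Section 8.11 | Agree? |
|---|---|---|---|
| Low neutrophils or platelets | "ixazomib may be reinitiated with 1 dose level reduction" | one level down | yes |
| Neuropathy, new Grade 1 with pain, or Grade 2 | unreduced | one level down | **no** |
| Neuropathy, Grade 2 with pain, or Grade 3 | "re-initiate ixazomib at the next lower dose level" | one level down | yes |
| Maculo-papular rash, Grade 2 or more, first occurrence | unreduced (9.9a: reduced) | one level down | **no** |
| Other related Grade 3 events | next lower dose | one level down | yes |

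Two of the five rows conflict. Neuropathy is the clean example, because the rash row is also at odds with 9.9a.

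**2. One event at two times.** Take Grade 2 neuropathy lasting 14 days (an assumed duration) in a patient on 4 mg.

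- Onset Day 29, last day 29 + 13 = 42. Days 29 and 36 are omitted. Ixazomib resumes on Day 43 at 4 mg, and the next cycle starts at 4 mg under both sections.
- Onset Day 64, last day 64 + 13 = 77. Days 64 and 71 are omitted. At the next Day 1 (Day 85), Table 8.3 gives 4 mg and 8.11 gives 3 mg, a difference of 1/4 = 25%.

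Both patients had the same grade, the same duration and two omitted doses.

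**3. Pembrolizumab.** Day 64 is the last infusion, so omitting it is always omission to the end of the cycle, even if the event clears before Day 85. Section 8.11 then leads to level -1: 2 of 4 infusions per cycle, or 50%. No row of Table 8.2 assigns that level.

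**4. How often the timing matters.** The documents give no event durations, so duration L is assumed. For onset day d from 1 to 84, a dose on day s is omitted if d ≤ s ≤ d + L − 1. The share is the number of onset days that cost the last dose of the cycle, divided by the number that cost any dose.

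| L (days) | Ixazomib (last dose Day 71) | Pembrolizumab (last dose Day 64) |
|---|---|---|
| 7 | 7/57 = 12% | 7/22 = 32% |
| 14 | 14/71 = 20% | 14/43 = 33% |
| 21 | 21/71 = 30% | 21/64 = 33% |
| 28 | 28/71 = 39% | 28/64 = 44% |
| 42 | 42/71 = 59% | 42/64 = 66% |

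These are shares of calendar days, not event probabilities. From 21 days for ixazomib and 28 for pembrolizumab, some late onsets also outlast Day 84 and would delay the next cycle. For ixazomib, the share matters only in the two conflicting rows.

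**The case against.** The best defense is that the headings divide the work. Tables 8.2 to 8.4 concern events during a cycle, 8.11 concerns the start of a new one, and so 8.11 simply governs Day 1. The text does not keep to that division. The neutrophil and platelet row of Table 8.3 itself fixes the dose for the following cycle. Table 8.2 often allows 12 weeks for resolution, which is 12 × 7 = 84 days, a whole cycle. The neuropathy exemption is tied to grade, not to position in the cycle. Section 8.0 tells staff to apply the largest reduction, but only when there are several adverse events.

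Other parts of the defense stand.

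- Table 8.2 and Section 8.11 can be read together, the former giving timing and the latter the level. A reader might infer that Table 8.2 orders a restart on the full schedule, but no row says so. Its pneumonitis and myocarditis rows also say to hold rather than omit, and the protocol defines these differently.
- A reader might infer that two Day 64 omissions would stop pembrolizumab. At level -1 there is no Day 64 infusion, so a second trigger would have to fall on Day 43. Several recurrences already mean permanent discontinuation under Table 8.2.
- The neuropathy row restarts below Grade 1 or at baseline, and 8.11 accepts Grade 1 or baseline. A reader might see a further contradiction, but both are met by applying the stricter condition to ixazomib.
- Treatment starts at Mayo Clinic institutions, local physicians may not treat, and enrollment is at most 41. This limits divergent practice but does not supply the missing rule.

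**Conclusion.** The point holds in a bounded form. There is an express contradiction on the ixazomib dose in two of the five Table 8.3 restart rows (4 mg against 3 mg for a patient on the starting dose), and the rash row has a second conflict with 9.9a. For pembrolizumab there is an unresolved interaction that can halve the scheduled infusions.

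Two wider readings are tempting but not supported. The first is that 8.11 contradicts the event tables in general: three ixazomib rows agree with it, as do the dexamethasone rows of Table 8.4 that omit and restart. The second is that the calendar day alone decides the dose. An early event that persists to the last dose triggers 8.11 too, so onset and duration act together.

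The neuropathy conflict follows from the text and assumes only that the omission reaches Day 71 and the event has resolved by the next Day 1. The shares of 12% to 59% and 32% to 66% rest on assumed durations of 7 to 42 days. How many patients would be affected cannot be derived from the documents.

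**What to change.** Reconcile Section 8.11 with Tables 8.1 to 8.3 and Section 9.9a so that each event leads to one dose instruction. The revised text should state:

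- whether 8.11 or the event row governs when the last dose or doses of a cycle were omitted;
- whether the 8.11 reduction applies only to the omitted drug;
- which Table 8.2 events, if any, lead to pembrolizumab level -1;
- one restart instruction for rash across Table 8.3, 8.11 and 9.9a.

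The choice of clinical rule is the sponsor's. The cost is a wording amendment to Sections 8 and 9.9a, with no added visits, tests or patients and no change to the statistical design.
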